6.1.1 Additional Information Regarding Safety Laboratory Assessments

Analysis of samples will be conducted by a central laboratory. Details regarding collection of samples, shipment of samples, reporting of results, laboratory reference ranges, and alerting abnormal values will be supplied to the site before site initiation in a Study Laboratory Manual. The results of the analysis will be made available to each site by the central laboratory.

Additional and repeat laboratory safety testing may be performed locally at the discretion of the Investigator. As local laboratory data will not be collected in the electronic case report form (eCRF), if feasible, a sample should also be sent to the central laboratory.

Investigators will be asked to comment on those abnormalities on the respective laboratory result page, including a notation of the clinical significance of each abnormal finding in the subject's source documents. The laboratory sheets will be filed with the subject's source documents. Reporting of laboratory AEs is described in Section 10.3.

6.1.2 Screening Failures and Rescreening of Potential Subjects

A screen failure is defined as a subject who has given informed consent/assent and failed to meet the inclusion and/or exclusion criteria. Subjects who initially fail to meet the inclusion/exclusion criteria may be re-screened as per the assessment of the Investigator. Subjects who are re-screened will be required to be re-consented and have all required Screening Visit procedures performed.

6.1.2.1 Rescreening of Subjects Who Develop COVID-19 During the Screening Period

[figure not shown]
Although molecular testing for asymptomatic COVID-19 infection is not required in this study, some subjects may develop suspected or confirmed symptomatic COVID-19 infection, or it is discovered that subjects have asymptomatic COVID-19 infection during the Screening Period. In such cases, subjects may be considered eligible for the study after meeting all Inclusion/Exclusion Criteria related to active infection, and after meeting the following criteria:

- At least 10 days (20 days for severe/critical illness) have passed since symptoms first appeared or positive test result, and
- At least 24 hours have passed since last fever without the use of fever-reducing medications, and
- Symptoms (eg, cough and shortness of breath) have resolved and
- In the opinion of the Investigator, there are no COVID-19 sequelae that may place the subject at a higher risk of receiving investigational treatment, and
- Negative follow-up molecular test for COVID-19 based on institutional, local or regional guidelines

6.2 Induction Phase and Maintenance Phase Treatment Period

On Day 1, prior to randomization in the Induction Phase, the baseline assessments (including laboratory assessments), as shown in [Table 4](#), will be completed. The Investigator will review all available information to confirm subject eligibility.

- Screening laboratory tests will be used to determine eligibility for randomization with the exception of pregnancy tests, which will need to be confirmed by the Day 1 test results.
- A urine (or serum) pregnancy test must be performed for all females of childbearing potential on Day 1 and the results reviewed prior to randomization. A negative pregnancy test result must be obtained prior to randomization. If the urine pregnancy test result is positive but this is believed to be a false positive, the site may perform a stat serum pregnancy test at the local laboratory to confirm pregnancy status.
- Baseline laboratory tests will be performed on Day 1 for comparison with follow-up tests. However, the results of these tests will not be available prior to randomization on Day 1.

After eligibility has been confirmed and baseline assessments have been completed, eligible subjects will be randomized to treatment on Day 1. The first 3 weekly SC doses will be administered in the clinic. Subjects will remain in the clinic for at least 30 minutes following dosing for observation. Subsequent visits, assessments and procedures will be performed as per the Table of Events ([Table 4](#) for the Induction Phase and [Table 5](#) for the Maintenance Phase).

[figure not shown]
For the Maintenance Phase, the assessments performed at the Week 24 Visit (Visit 8) of the Induction Phase will also serve as the data for the Maintenance Phase Week 24 Visit (Visit 8) and

do not need to be repeated specifically for the Maintenance Phase. If the Maintenance Phase Week 24 Visit, the first day of the Maintenance Phase, does not occur at the Induction Phase Week 24 Visit (Visit 8), an assessment of concomitant medications and AEs/SAEs will be performed, and a urine pregnancy test (in FCBP only) will be conducted if it has been more than 30 days since the last test. The Investigator will confirm subjects meet the criteria to enter the Maintenance Phase according to Section 6.4.2.8. A +4 day allowance (in addition to the Visit 8 window of +/-3 days) for the scheduling of the EGD and Investigator assessment of subject suitability for entry to Maintenance is available if needed.

[figure not shown]
If subjects are out of window for their Week 24 dose due to use of the additional +4 day window for the EGD, subjects should skip the Week 24 dose and take the Week 25 dose which will be their first Maintenance Phase dose.

The following will be performed during the Induction Phase and Maintenance Phase Treatment Periods as specified in the Table of Events detailed in [Table 4](#) and [Table 5](#):

- Assessment of inclusion/exclusion criteria to confirm eligibility (Day 1 only)
- Concomitant therapy
- Assessment of AEs/SAEs
- Hematology, chemistry, and urinalysis
- Urine pregnancy test (only for FCBP)
- Physical examination
- Height and weight
- Vital signs
- Serum antibodies to CC-93538
- Serum CC-93538 PK assessment

- Modified Daily Symptom Diary (mDSD)
- Phone call reminder for mDSD completion (just prior to Week 22 and Week 46)

- EGD with tissue biopsies
- EoE Endoscopic Reference Score (EREFs)
- Entry to the Maintenance Phase assessment (only at Induction Phase Week 24)
- IP administration

Refer to Section [6.4](#) for a description of the efficacy assessments conducted throughout the study.

6.2.1 EoE Flare Assessment Visit

Subjects with a worsening of EoE symptoms during the study, either in the Induction Phase or Maintenance Phase will be required to complete the EoE Flare Assessment Visit as shown in the Table of Events ([Table 4](#) and [Table 5](#)). Subjects with increased signs and symptoms of EoE are instructed to contact the Investigator and/or study staff to determine if an EoE Flare Assessment Visit is warranted. An EoE Flare Assessment Visit should be scheduled as close as possible to the time that an EoE flare is suspected.

Any worsening of EoE symptoms during study participation will be documented as an EoE flare. See Section [6.4.2.7](#) for the protocol definition of EoE flare and EoE Flare Assessment Visit details.

In the event that subjects discontinue the study prematurely due to an EoE flare, the ET Visit will also be completed, but procedures performed at the EoE Flare Assessment Visit do not need to be repeated for the ET Visit.

If subjects had an EGD performed for an EoE flare assessment during the Induction (prior to Week 24) or Maintenance (prior to Week 48) Phases, an EGD will also be performed at Week 24 or 48, respectively. However, an exception will be made if in the Investigator's judgement the EoE flare assessment occurred too close to Week 24 or Week 48 such that it is considered unsafe to perform another EGD within this short interval. In these cases, a discussion with the Medical Monitor will take place well in advance of the Week 24 or Week 48 Visit.

The following evaluations will be performed as specified in [Table 4](#) and [Table 5](#):

- Concomitant therapy
- Assessment of AEs/SAEs
- Hematology, chemistry, and urinalysis*
- Weight
- Vital signs

* Note that these samples do not need to be a pre-dose draw unless the subject is expected to dose later that day.

- EGD with tissue biopsies **
- EoE Endoscopic Reference Score (EREFs) **

Refer to Section [6.4](#) for a description of the efficacy assessments conducted throughout the study.

6.2.2 *End of Treatment/ Early Termination (ET) Visit*

For subjects who discontinue the study prematurely for any reason (ie, subjects that do not complete Week 48), every attempt should be made to complete the assessments detailed in the ET Visit conducted as close as possible to the time of study discontinuation. If study discontinuation occurs at the regularly scheduled visit (eg, Induction Phase Week 12 or Maintenance Phase Week 36), the ET Visit and all corresponding ET Visit procedures should be conducted ([Table 4](#) and [Table 5](#)). In addition, these subjects should return for the Safety Follow-up Visit (Section [6.3.1](#)). Subjects who complete the Induction Phase Week 24 Visit but do not continue in the Maintenance Phase or OLE study should complete the Week 24/ET Visit and return for the Interim 8-week and Final 16-week Safety Follow-up Visits at Week 31 and Week 39, respectively (Section [6.3.1](#)). Subjects who complete the Induction Phase and enter the OLE study should complete the Week 24/ET Visit; these subjects do not need to return for the 2 Safety Follow-up Visits. Assessments conducted at the Week 24 Visit do not need to be repeated. Subjects who complete the Maintenance Phase Week 48 but do not continue in the OLE study should return for the Interim 8-week and Final 16-week Safety Follow-up Visits at Week 55 and Week 63, respectively. For subjects who are discontinuing the study prematurely due to an EoE flare, ET procedures performed at the EoE Flare Assessment Visit do not need to be repeated.

The following evaluations will be performed as specified in [Table 4](#) and [Table 5](#):

[figure not shown]
- Concomitant therapy
- Assessment of AEs/SAEs (monitored through 16 weeks after the last dose of IP or the Final Safety Follow-up Visit, whichever is longer)
- Hematology, chemistry, and urinalysis
- Pregnancy test (only for FCBP)
- Physical examination
- Height and weight

** Note that EGD is required at EoE Flare Assessment Visits to determine if use of rescue therapy is clinically indicated. Alternatively, if endoscopy is conducted as part of an emergency department visit or hospitalization for the EoE flare, medical record source data should be collected for the EoE Flare Assessment Visit EGD requirement. In addition, all attempts should be made to collect biopsy samples, and these samples should be sent to the central reader for histologic analysis.

- Vital signs
- Serum antibodies to CC-93538
- Serum CC-93538 PK assessment

- Modified Daily Symptom Diary (mDSD)

- EGD with tissue biopsies*
- EoE Endoscopic Reference Score (ERES)*

Refer to Section [6.4](#) for a description of the efficacy assessments conducted throughout the study.

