3.1.5 Worsening of EoE Symptoms

Subjects with a worsening of EoE symptoms during the study, either in the Induction Phase or Maintenance Phase will be required to complete the EoE Flare Assessment Visit per the Table of Events ([Table 4](#) and [Table 5](#)). For subjects with a worsening of EoE symptoms, an EGD will be required to determine if rescue therapy is clinically indicated. Subjects with increased signs and symptoms of EoE are instructed to contact the Investigator and/or study staff to determine if an EoE Flare Assessment Visit is warranted.

Any worsening of EoE symptoms during study participation will be documented as an EoE flare. See Sections [6.4.2.7](#) and [6.2.1](#) for the protocol definition of EoE flare and EoE Flare Assessment Visit details, respectively.

Subjects experiencing a severe EoE flare in the Induction or Maintenance Phase may continue to participate with concomitant rescue therapy as needed and will be eligible to enter the OLE study only following completion of Week 24 of the Induction Phase or Week 48 of the Maintenance Phase, respectively (refer to Section 6.4.2.7 for details). Subjects with a severe EoE flare in the Induction Phase will not qualify for entry into the Maintenance Phase.

Subjects experiencing a mild to moderate EoE flare in Induction will continue on into the Maintenance Phase of the study and will be eligible to enter the OLE study following the completion of the Week 48 Visit.

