Further assessment of the psychometric properties of the mDSD in a Phase 3 study will include a preliminary blinded analysis after the first one-third of subjects complete 24 weeks of treatment in the Induction Phase as well as a final analysis, in all subjects completing Week 24, at the end of the study. These analyses will focus on the reproducibility, validity, and responsiveness of the DD and mDSD composite score endpoints as well as confirmation of the clinically meaningful response definition for the clinical co-primary endpoint, mean change in DD from baseline to Week 24, as described in a separate Psychometric Analysis Plan. The reproducibility of the mDSD will be assessed among “stable” subjects (ie, those reporting no change in [REDACTED] rating at Week 2) using 2 consecutive 14-day periods, the final 14-days of screening (baseline) and Weeks 1 to 2.

6.4.2.7 *Worsening of EoE Symptoms, EoE Flare, and the EoE Flare Assessment Visit*

Subjects with a worsening of EoE symptoms during the study, either in the Induction Phase or Maintenance Phase will be required to complete the EoE Flare Assessment Visit as shown in the Table of Events ([Table 4](#) and [Table 5](#)). Subjects with increased signs and symptoms of EoE are instructed to contact the Investigator and/or study staff to determine if an EoE Flare Assessment Visit is warranted.

An EoE Flare Assessment Visit including safety and efficacy evaluations can occur at any time during the study. An EGD is required at EoE Flare Assessment Visits to determine if use of rescue therapy is clinically indicated. Alternatively, if endoscopy is conducted as an intervention during an emergency department visit or hospitalization for a worsening of EoE symptoms or flare, medical record source data including details of the endoscopic procedure should be collected for the EoE Flare Assessment Visit EGD requirement. In addition, all attempts should be made to collect biopsy samples, and these samples should be sent to the central reader for histologic analysis.

The Investigator will confirm if the worsening of EoE symptoms requires rescue therapy and, thus, is deemed a severe EoE flare according to the following protocol definitions.

Any worsening of EoE symptoms during study participation will be documented as an EoE flare.

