- A severe EoE flare is defined as any worsening of EoE symptoms including a high intensity episode resulting in emergency department visit or hospitalization, with the need for endoscopic intervention (eg, for prolonged food impaction) and/or need for rescue therapy (eg, including but not limited to corticosteroid therapy or dilation), or a worsening of EoE symptoms resulting in the need for rescue therapy only without endoscopic intervention.
- A mild to moderate EoE flare is defined as any worsening of EoE symptoms without the need for rescue therapy or endoscopic intervention.

ET procedures performed at the EoE Flare Assessment Visit do not need to be repeated for subjects who discontinue the study prematurely due to an EoE flare.

Induction Phase

In the Induction Phase, if a subject experiences a severe EoE flare requiring intervention with endoscopy and/or treatment with any rescue therapy (eg, including but not limited to systemic or swallowed topical corticosteroid therapy or dilation), the subject may continue participation in the Induction Phase with concomitant rescue therapy as needed until completion of the Induction Phase at Week 24. The subject will not meet the entry criteria for the Maintenance Phase. The subject will be eligible to enroll in the OLE Study, CC-93538-EE-002, based on the judgement of the Investigator after completing Week 24 of the Induction Phase.

Subjects participating in the Induction Phase who require pharmacotherapy or dietary modifications prohibited by the protocol that may affect CC-93538 efficacy assessment or a dilation procedure will not be eligible for entry into the Maintenance Phase. Refer to Maintenance entry criteria in Section [6.4.2.8](#).

Maintenance Phase

In the Maintenance Phase, if a subject experiences a severe EoE flare requiring intervention with endoscopy and/or treatment with any rescue therapy (eg, including but not limited to systemic or swallowed topical corticosteroid therapy or dilation), the subject may continue participation in the Maintenance Phase with concomitant rescue therapy as needed until completion of the Maintenance Phase at Week 48. The subject will be eligible to enroll in the OLE Study, CC-93538-EE-002, based on the judgement of the Investigator after completing the study (Week 48).

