The following sensitivity analyses will be performed to support the main estimand analysis and provide additional insights to understand the treatment effect:

- Robustness due to missing data MI under MAR assumption will be explored using tipping point analysis ([Yan, 2009](#); [Campbell, 2011](#); [Yuan, 2014](#)).
- A minimum of 4 measurable diary days per week is required to derive a DD score for the 14-day period. The analysis method will be the same as the primary analysis.

In considering the ICEs of study interest (ie, ICE number 2, use of rescue therapy/prohibited medication), supplementary analyses will be performed using the treatment policy estimand strategy and a hypothetical estimand strategy. In addition to the overall population, change in DD from baseline to Week 24 will be analyzed in the Steroid Inadequate Responders/Intolerant subgroup. This analysis will be similar to the overall population except that the ANCOVA model will not include Steroid Inadequate Responders/Intolerant status. See Section [9.6.4](#) for details on the hierarchical testing procedure to control the Type I error rate.

9.6.1.3 *Eosinophilic Histologic Response at Week 24 (Induction Phase)*

The other co-primary endpoint, eosinophilic histologic response, is defined as a peak esophageal eosinophil count $\leq 6/\text{hpf}$ (across all available esophageal levels) at Week 24.

The primary analysis of the eosinophilic histologic response will be conducted on the ITT population using the CMH test at a 2-sided 5% significance level, stratified by Steroid Inadequate Responders/Intolerant status. For treatment comparison between CC-93538 360 mg SC once weekly and placebo, the 2-sided 95% CI for the difference in proportions using the CMH weights and the 2-sided p-value from the CMH test will be provided.

Missing data in subjects without use of rescue therapy/prohibited medication prior to Week 24 will be handled using a multiple imputation (MI) approach ([SAS Institute, 2015](#)) under a missing at random (MAR) assumption.

A sensitivity analysis will be performed using tipping point analysis to assess the robustness of the primary efficacy analysis with regards to handling of missing data.

In considering the ICEs of study interest (ie, ICE number 2, use of rescue therapy or prohibited medication which may impact the efficacy assessment), a supplementary analysis using the treatment policy estimand strategy for the histologic endpoint at Week 24 will be conducted.

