9.6.2 Analysis of Key Secondary Efficacy Endpoints

For the first key secondary endpoint, proportion of subjects achieving eosinophilic histologic response defined as a peak esophageal eosinophil count < 15/hpf (across all available esophageal levels) at Week 24, the main analysis will be conducted based on the ITT population using the same type of method as described for the histologic response at Week 24 (the co-primary endpoint). The same summary and inferential statistics will be reported as specified for the primary analysis of the co-primary endpoint of histologic response in Section [9.6.1.3](#). Missing data and ICEs of interest will be handled via the same strategy as for the primary analysis of the co-primary endpoint of histologic response.

For the second key secondary endpoint, mean change in the endoscopic features of EoE as measured by the EoE Endoscopic Reference Score (EREFS) from baseline to Week 24, the main analysis will be conducted based on the ITT population using an ANCOVA model with treatment group, Steroid Inadequate Responders/Intolerant status (yes or no), and baseline EREFS values included in the model. The same summary and inferential statistics will be reported as specified for the primary analysis of the co-primary endpoint of change in DD in Section [9.6.1.2](#). Missing data and ICEs of interest will be handled via the same strategy as for the primary analysis of the co-primary endpoint of change in DD.

For the third key secondary endpoint, mean change in the mean adjusted histology grade score as measured by the scoring system (EoEHSS) from baseline to Week 24, the main analysis will be conducted based on the ITT population using an ANCOVA model with treatment group, Steroid Inadequate Responders/Intolerant status (yes or no), and baseline mean adjusted histology grade score values included in the model. The same summary and inferential statistics will be reported

as specified for the primary analysis of the co-primary endpoint of change in DD in Section 9.6.1.2. Missing data and ICEs of interest will be handled via the same strategy as for the primary analysis of the co-primary endpoint of change in DD.

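### If the Week 24 or Week 48 EGD is waived because a flare EGD was too recent, does it matter that the protocol does not say which reading is analysed?

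*Combined protocol and SAP*

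**What the plan says.** Section 6.2.1 sets the default that a flare EGD does not replace the Week 24 or Week 48 EGD. The exception is where "the EoE flare assessment occurred too close to Week 24 or Week 48 such that it is considered unsafe to perform another EGD", and what then follows is a discussion with the Medical Monitor. No interval in days is given. Reuse of flare procedures is stated only for early termination: "procedures performed at the EoE Flare Assessment Visit do not need to be repeated for the ET Visit".

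Flare assessments produce endoscopy data. Section 3.1.5 states: "For subjects with a worsening of EoE symptoms, an EGD will be required to determine if rescue therapy is clinically indicated". For endoscopies done in an emergency or hospital setting, Section 6.4.2.7 adds that "all attempts should be made to collect biopsy samples, and these samples should be sent to the central reader for histologic analysis". Not every flare leads to rescue: "A mild to moderate EoE flare is defined as any worsening of EoE symptoms without the need for rescue therapy or endoscopic intervention" (Section 6.4.2.7).

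On the analysis side, Section 9.6.1.3 states: "Missing data in subjects without use of rescue therapy/prohibited medication prior to Week 24 will be handled using a multiple imputation (MI) approach", under MAR. It also states: "A sensitivity analysis will be performed using tipping point analysis to assess the robustness of the primary efficacy analysis" with regard to missing data. For each key secondary endpoint, Section 9.6.2 says: "Missing data and ICEs of interest will be handled via the same strategy as for the primary analysis" of the matching co-primary endpoint. Section 9.6.3 carries the missing-data approach to Week 48. Under Table 8, a subject with rescue or prohibited medication that may affect efficacy (intercurrent event 2) counts as a histologic non-responder at Week 24.

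**The concern.** The protocol permits a missing endpoint value in subjects whose symptoms have just worsened, and says nothing about the reading taken shortly before. If the value is treated as missing, a subject without intercurrent event 2 goes to imputation under MAR. That assumption is least comfortable here, because the EGD is absent on account of a flare. Section 9 does not list the imputation variables, so flare status cannot be assumed to be among them.

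The endpoints touched are the histologic co-primary, four of the five key secondary endpoints (below 15/hpf, EREFS, EoEHSS grade and EoEHSS stage) and the EGD-based endpoints at Week 48. Several of these are in the confirmatory sequence of Section 9.6.4. A tipping point analysis is named for the co-primary endpoints only. The diary endpoints are unaffected.

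The fear is that imputing such subjects at their arm's general response rate would flatter the active arm, or that the choice between the two readings would be made after the data are known.

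**Working it through.** **The plan's own figure.** Inputs from Section 9.3: 212 and 106 subjects after 20% dropout, response 0.20 against 0.05, two-sided alpha 0.05, chi-square test.

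- Pooled rate: (212 × 0.20 + 106 × 0.05) / 318 = 0.15.
- SE under the null: √[0.15 × 0.85 × (1/212 + 1/106)] = 0.0425.
- SE under the alternative: √[0.20 × 0.80/212 + 0.05 × 0.95/106] = 0.0347.
- z = (0.15 − 1.96 × 0.0425) / 0.0347 = 1.92, so power is 97.3%. The stated figure of at least 90% holds.

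**Who is affected.** All of the following must be true:

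- The flare EGD falls before the visit window, that is before Day 166 (169 − 3) or Day 332 (337 − 5).
- It is nevertheless so close that a repeat is judged unsafe.
- No rescue or prohibited medication that may affect efficacy has been used.

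At Week 24 the EGD may also be done up to 7 days late (Table 4, note d), which leaves room to separate the two procedures. Section 6.4.2.8 uses the Week 24 endoscopy to judge entry to Maintenance, a further reason to perform it.

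**Size of the shift.** The waiver rate is not in the documents, so it is assumed. Let w be the share of an arm waived, p the response rate among the others, and r the true response of waived subjects relative to p. Imputation at the arm rate gives p, and the true arm rate is (1 − w)p + w·r·p, so the arm is overstated by w(1 − r)p. The net shift in the difference is (1 − r)(w_A·p_A − w_P·p_P). With p_A = 0.20 and p_P = 0.05:

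| w active / placebo | r | Shift (points of 15) |
|---|---|---|
| 1% / 1% | 0 | 0.15 |
| 2% / 2% | 0 | 0.30 |
| 5% / 5% | 0 | 0.75 |
| 5% / 5% | 0.5 | 0.375 |
| 1% / 3% | 0 | 0.05 |
| 2% / 5% | 0 | 0.15 |
| 1% / 5% | 0 | −0.05 |
| 5% / 1% | 0 | 0.95 |

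The largest entry is 0.05 × 0.20 − 0.01 × 0.05 = 0.0095. Against the SE of 3.47 points this is 0.95/3.47 = 0.27 of a standard error, and it needs flares near the visit to be five times as common on active treatment as on placebo. A 5% waiver rate means about 13 active subjects (0.05 × 266 = 13.3) and 7 placebo subjects (0.05 × 133 = 6.65).

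A higher active response does not alter the proportion. At 60% against 5%, with 5% waived in each arm, the shift is 0.05 × 55 = 2.75 points of 55, the same 5% relative change as 0.75 of 15.

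**Power if the waived subjects count as non-responders.** With 5% in each arm, the rates become 0.95 × 0.20 = 0.19 and 0.95 × 0.05 = 0.0475. The same formula gives z = (0.1425 − 1.96 × 0.0416) / 0.0340 = 1.80, or 96.4%.

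**The case for a change.** The best case for a change is that it costs almost nothing. One visit-mapping rule, one term in the imputation model and one count by arm would settle, before unblinding, which of two values enters a set of confirmatory endpoints. Central eosinophil readings are blinded (Section 6.4.1), and a recent observed value has an obvious claim over an imputed one. For the key secondary and Week 48 endpoints, Section 9 names no analysis that departs from MAR.

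What stands is that Section 9 is silent on the point and that MAR is less secure in this group. The rest is weaker.

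- The step from waived to missing rests on the visit-scheduling windows in Tables 4 and 5. Nothing in the text makes these analysis windows, and the text neither allows nor forbids mapping the flare EGD to the visit.
- Visit mapping and imputation variables are details that Section 9.1 assigns to the SAP.
- Substitution is not plainly better. A window reaching back to Week 20 or Week 44 would carry forward a reading up to four weeks old, taken because the subject was flaring, into an endpoint defined at the visit. EREFS is scored by the investigator (Section 6.4.1), so the argument from a blinded central reading does not cover it.
- Worsening symptoms do not establish histologic non-response. Section 1.3.3 reports that 180 mg weekly had a histologic effect without a clinical one, so r = 0 is an extreme assumption.

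**Conclusion.** No change to the plan follows. This is an unstated detail that an analyst would settle in the ordinary visit-mapping and imputation specifications, and both reasonable choices lead to nearly the same result. Under the assumed waiver rates of 1% to 5% per arm, with every waived subject taken as a true non-responder, the histologic difference moves by between −0.05 and +0.95 of 15 points, and power in the 5% case stays above 96%. The planned tipping point analysis already covers the co-primary endpoint, where a departure from MAR would matter most.

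The conclusion rests on waivers being rare. The documents do not give the rate, but the conditions in Section 6.2.1 point that way. It also rests on the mapping being settled before unblinding, as is normal for such conventions. The arithmetic covers the histologic co-primary at the planning rates; for EREFS, EoEHSS and the Week 48 endpoints, the expectation of a small effect rests on the same small group and was not calculated. Whether a repeat EGD is safe remains a clinical judgement and is not in question here.
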